#### 2.7.3 Supervision and monitoring.

Clinicians will receive weekly supervision as outlined above. Besides supervision, several sessions audio-recorded sessions will be analyzed by another founder of MIT to assess adherence to MIT/CBT-F.

In each experimental condition all treatment sessions will be recorded. In order to analyze the therapeutic processes, sessions will be chosen at random for each of the two groups. Transcription of the sessions will be then analyzed in order to explore the process of change mechanisms.

#### 3. Statistical analysis

As a feasibility study, analyses will be mainly focused on a descriptive method. However, in order to assess whether the experimental condition including MIT sessions leads to a reduction in eating disorder there will be also carry out an intention-to-treat and per-protocol analyses in order to determine treatment effects on all the outcome measures, adjusting for pre-specified baseline covariates. An exploratory repeated measures regression model, adjusting for baseline measures, will be adopted to assess the treatment effects on the outcomes and their effects over time. There will be also explored the sub-scales measures in order to assess whether there might be any treatment signals within sub-scales. Estimates of treatment differences and associated standard errors will be obtained from the mixed-effects models analyses. These will be run for intention-to-treat and per protocol analyses.

Exploratory linear multiple regressions, in which all predictors and covariates will be entered independently into the regression algorithm to avoid artificial inflation of estimated R2, these will be adopted to investigate the mediational effects of the putative underlying mechanisms of change. Finally, number of sessions received will be examined as a putative moderator.

Upon completion of the trial additional exploratory analyses will be run, from sub-samples of good and poor outcomes to identify mechanisms of change.

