### 2.2 Study design

A parallel-group randomized controlled trial design will be used in order to compare CBT-E (n = 10) condition to combined MIT/CBT-F (n = 10). Patients in both conditions will receive 20 weekly sessions of either CBT-E or MIT/CBT-F.

Primary outcomes will be represented by ED and comorbid symptoms as assessed with the Eating Disorder Examination Questionnaire (EDE-Q6) (Fairburn & Beglin, 1994), which are expected to be

reduced after treatment. Other measures of ED and comorbid symptoms will still be considered primary outcomes. Secondary outcomes are anxiety, depression and global psychological symptoms. Lastly, exploratory outcomes will be difficulties in the emotional sphere such as understanding, processing, regulating or describing emotions.

Predictors, mediators and outcome variables will be measured at baseline, after 10 sessions with the exclusion of SCID-5 Interview, at the end of the treatment, and in the following 3, 6, 12, 18 and 24 months after the treatment. Two psychotherapies for each arm will be randomly selected, audio recorded and later analysed in order to explore the therapy process.

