#### 2.4 Participants

Twenty consecutive participants will be recruited at the CTI Disturbi Alimentari e Obesità. All participants will be aged 18 years or over and treatment-naive. They will be screened for a main diagnosis of ED in the past 6 months. Inclusion and exclusion criteria are reported in Table 1.

Inclusion Criteria	Exclusion Criteria
Aged >18 years	Acute psychotic episode, psychotic symptoms, Bipolar I disorder; antisocial personality disorder
ED diagnosed in the past 6 months	Suicidal ideation
Seeking treatment for eating disorder	Substance abuse
Able to provide written, informed consent	Previous psychological intervention for other eating disorders
BMI > 18.5	Currently involved in other ongoing treatment

Table1 Inclusion and Exclusion Criteria

All participants meeting inclusion criteria will be informed about the trial and will decide whether to take part. A regular ED-focused treatment will be offered to all participants excluded from the trial or who decline participating. All participants will give written informed consent before participation.

Drop-out rates from each arm will be reported for patients withdrawing during treatment and those lost to follow-up. Treatment is delivered in a private center therefore participants are paying for their care, however there is no financial incentive to participate in the trial. The study protocol is written in accordance with the European Union Standards of good clinical practice and in accordance with the Declaration of Helsinki. The protocol has been approved by the Ethics Committee of the Department of Dynamic and Clinical Psychology of "La Sapienza" University (Rome) Prot. n. 0000781, 05/13/2022 - [UOR: SI000092 - Classif. VII/15]

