#### 4. Discussion

Patients with EDs have a number of psychotherapeutic options, particularly CBT-E, but nonresponse, partial response and dropout remain challenges for treatment. We proposed that adding treatment components focusing on poor metacognition (the capacity to make sense of mental states and use psychological knowledge to promote emotion regulation; Dimaggio & Lysaker, 2010; Semerari et al., 2003; 2014) and maladaptive interpersonal schemas would offer adjunctive therapeutic options to address problematic eating behaviors. In this pilot RCT we considered these components from MIT as a bolt-on to a commonly used, empirically validated psychological intervention (CBT-E).

We hypothesize that the CBT-F+MIT arm will result as highly tolerable in terms of session attendance and dropouts. We expect possible <10-15% dropouts which would be above the average 17.51% found across evidence-based treatments (Grenon et al., 2019). Low dropout rate is a feature of existing MIT protocols for complex mental health problems such as personality disorders, psychosis, either as a solo treatment (Dimaggio et al., 2017; Gordon-King et al., 2018; Inchausti et al., 2018, 2020; 2022; Popolo et al., 2018; 2019; 2021; Simonsen et al., 2021) or combined with other treatments such as combining metacognition-based interventions with compassion focused practices (Cheli et al., 2022).

The main limitations of this pilot RCT are the small sample, with only 20 patients randomized to either of the 2 arms, possibly limiting scope to observe treatment specific effects. That said use of mixed effects modelling and confidence interval derived analyses may mitigate this problem. The trial will be an initial test of this new treatment combination. Further studies with larger samples and other ED based presentations will be warranted.

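### Section 3 says its entry rule avoids an inflated R2 in the exploratory mediation regressions; with 20 patients and all terms entered together, raw R2 is still inflated

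*Combined protocol and SAP*

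**What the plan says.** Section 3 (Statistical analysis) describes "Exploratory linear multiple regressions" in which "all predictors and covariates will be entered independently into the regression algorithm to avoid artificial inflation of estimated R2". Their purpose is mediation: "these will be adopted to investigate the mediational effects of the putative underlying mechanisms of change".

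The sample is small. Section 2.4 states: "Twenty consecutive participants will be recruited at the CTI Disturbi Alimentari e Obesità". Section 2.2 splits them 10 and 10.

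The terms of these models are not given. Section 2.2 says "Predictors, mediators and outcome variables will be measured at baseline, after 10 sessions with the exclusion of SCID-5 Interview", but it does not say which measures are predictors and which are mediators. Section 3 speaks of "adjusting for pre-specified baseline covariates" for the intention-to-treat and per-protocol analyses, but no list of covariates appears anywhere. The plan does not mention adjusted R2, shrinkage, cross-validation, stepwise selection or an estimator of the indirect effect.

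**The concern.** The sentence promises that a way of entering variables protects against an inflated R2. With 20 patients that promise matters, because ordinary R2 rises with every term added, whether or not the term is related to the outcome. If the promise is not true, a reader who meets a sizeable R2 in the results may take it as support for a mechanism of change when noise alone would produce much of it.

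The entry rule is also ambiguous. It can mean that all terms go into one model together, or that each term is fitted on its own. The two readings have different consequences both for R2 and for whether a mediated effect can be estimated.

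**Working it through.** The plan gives no R2, number of terms or sample-size calculation, so there is no figure of its own to reproduce.

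**Inputs**
- n = 20 (sections 2.2 and 2.4).
- n = 17 as a sensitivity case. Section 4 says "We expect possible <10-15% dropouts" about the CBT-F+MIT arm. Applying 15% to all 20 patients is an assumption: 20 × 0.85 = 17.
- p, the number of terms besides the intercept: not stated. Assumed range 3 to 8. For example, arm, baseline outcome and three process measures make p = 5.

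**Reading A: all terms entered together.** For least squares with an intercept and no true association, R2 follows a Beta(p/2, (n-p-1)/2) distribution with mean p/(n-1).

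| p | Mean R2, n = 20 | 95th percentile, n = 20 | Mean R2, n = 17 |
|---|---|---|---|
| 3 | 3/19 = 0.16 | 0.38 | 3/16 = 0.19 |
| 5 | 5/19 = 0.26 | 0.51 | 5/16 = 0.31 |
| 8 | 8/19 = 0.42 | 0.68 | 8/16 = 0.50 |

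Raw R2 cannot fall when a term is added, so among models built from the same set of terms this reading gives the largest raw R2.

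Adjusted R2 is 1 - (1 - R2)(n-1)/(n-p-1). Putting in the null mean p/(n-1) gives 1 - (n-1-p)/(n-p-1) = 0. The bias is removed by the adjustment, not by the order or manner of entry.

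**Forced entry against stepwise selection.** A null simulation (n = 20, 10 candidate terms, 1000 runs) compared forcing in all 10 with picking the best 3 by forward selection.

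| | Forced, 10 terms | Forward selection, best 3 |
|---|---|---|
| Mean raw R2 | 0.54 | 0.37 |
| Mean adjusted R2 | 0.02 | 0.26 |

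Forced entry therefore helps adjusted R2 but leaves raw R2 higher.

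**Reading B: one term at a time.** Each null R2 averages 1/19 = 0.05 (n = 20) or 1/16 = 0.06 (n = 17). The inflation is small in each model, but no model holds both arm and mediator. The arm-to-mediator effect and the total effect can still be estimated. The arm-adjusted mediator-to-outcome path, and with it the direct and indirect effects, cannot.

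As an illustration, suppose arm shifts mediator and outcome by 0.8 within-arm SD each, allocation is 1:1, and the mediator has no effect on outcome. The slope of outcome on mediator without arm is (0.25 × 0.8 × 0.8)/(1 + 0.25 × 0.8²) = 0.16/1.16 = 0.138, where the true value is 0. Multiplying by the arm-to-mediator effect gives a false indirect effect of 0.8 × 0.138 = 0.11. With arm in the model the expected slope is 0.

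**The case against.** The strongest defence is that the authors meant forced entry as opposed to data-driven selection. That rule does prevent one real form of optimism, as the adjusted R2 values of 0.02 and 0.26 show. This part stands. It does not rescue the sentence, which speaks of estimated R2 without qualification and mentions neither stepwise selection nor adjusted R2.

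A second defence is that these analyses are labelled exploratory, section 3 puts description first, and section 4 names the small sample as the main limitation. This also stands and limits the weight of the point. The mitigation that section 4 offers, mixed models and confidence intervals, does not deal with R2 in these regressions.

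A reader might infer more than the documents support, in three ways.
- *That the plan cannot estimate mediation at all.* This follows only from one-at-a-time entry. The text calls these multiple regressions containing all predictors and covariates, so joint entry is the likelier reading, and under it arm and mediator can share a model.
- *That all 11 listed instruments would be predictors, with an expected null R2 of 11/19 = 0.58.* Section 2.5 introduces them as measures of the outcomes. They include the EDE-Q6, which section 2.2 names as the primary measure, so a count of 11 is not credible.
- *That the pilot will declare a mechanism because of a high R2.* No section states such a rule.

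**Conclusion.** The concern holds in a limited form. On the likelier reading, the stated protection is not true of raw R2: noise alone gives an expected value of 0.16 to 0.42 for 3 to 8 terms at n = 20. The size depends on the assumed number of terms, but the direction is the same for any number from one upwards. On the less likely reading the inflation per model is slight, but the indirect effect is lost. Nothing else in the document defines the entry rule or supplies a corrected measure of fit.

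The point is minor. It bears on how the exploratory mechanism results are read. It does not touch the comparison of the two arms, which section 3 takes from the mixed-effects models.

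**What to change.** Rewrite the paragraph in section 3 as follows.
- Delete the clause that gives avoidance of R2 inflation as the reason for the entry rule.
- Name the mediators, and state that each is examined in its own model with arm, mediator, baseline outcome and baseline mediator entered together. That is 4 terms, leaving 20 - 4 - 1 = 15 residual degrees of freedom if all 20 patients are observed.
- Report the arm-to-mediator path, the arm-adjusted mediator-to-outcome path, and their product (the indirect effect) with a bootstrap or Monte Carlo 95% confidence interval.
- State that raw R2 will not be used as evidence of a mechanism. Even this 4-term model has a null mean of 4/19 = 0.21. If a measure of fit is wanted, give adjusted or leave-one-out R2.

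No new data are needed, since the questionnaires are already scheduled at baseline, after 10 sessions and at end of treatment. The authors do have to choose and name the mediators. The reported fit will look smaller and the intervals will be wide. In a simulation of the 4-term model at n = 20, with an assumed arm-to-mediator effect of 0.8 and mediator-to-outcome slope of 0.4 (true indirect effect 0.8 × 0.4 = 0.32), the bootstrap interval averaged about 1.4 wide and excluded zero in 13% of 400 trials. The change makes the mechanism analysis honest about its precision; it does not make it powerful.

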### Method/Design

### 2.1 Aims and hypotheses

The study is a pilot randomized controlled trial that aims to evaluate the feasibility and effectiveness of weekly MIT in addiction to CBT-F in a group of adults diagnosed with ED. Specifically, we will investigate in a sample of non-underweight adults presenting with ED whether once compared to CBT-E, a treatment combining MIT and CBT-F is a) feasible, b) well-tolerated and c) potentially effective on eating disorders symptoms and other outcomes. The study is defined according to the Standard Protocol Items: Recommendations for Interventional Trials (SPIRIT) statement and guidelines (Chan et al., 2013).

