## 2.7 Procedure

Treatment-seeking participants at the CTI Disturbi Alimentari e Obesità will first receive an assessment screening visit. Once evaluated for inclusion/exclusion criteria, they will be informed about the study. If they wish to participate, they will be required to give written informed consent.

Tab.1. Flow chart of the study design

The researcher will ensure that the person is fully informed of the randomization process and their chances of receiving additional MIT sessions. Once informed and written consent has been obtained, baseline measures about primary and secondary outcomes will be completed.

Participants will then be randomized into two experimental conditions: CBT-F+MIT (experimental treatment) and CBT-E (standard treatment). All participants in each experimental condition will first receive two initial standard sessions mainly focused on investigating the compliance to the treatment and on understanding the maintenance factors of the ED.

**2.7.1. Experimental Treatment:** Participants in the CBT-F+MIT condition will receive a total of 20 sessions over 20 weeks. Specifically, 2 sessions will be based on CBT-F as usual only. During these sessions participants will receive psychoeducational training on eating behaviors and an introduction to the protocol tools, namely the monitoring form, weight chart, transdiagnostic formulation and Eating Problem Check List (EPCL).

These elements will be used at the beginning of the remaining 18 sessions, in order to monitor the regulations of eating behaviors as well eliciting narrative episodes. These materials will form the basis for the MIT-part of the session, in which therapists will seek to form with the patient a shared understanding of the psychological reasons underlying their ED symptoms and their maladaptive interpersonal functioning. Once a shared understanding is reached, patients and therapist will work to develop healthier strategies for managing negative thoughts and feelings antecedent to disordered eating. They will also develop new strategies for engaging in social interactions that meet their

relational basic wishes, such as attachment, personal worth, autonomy and group belonging (Dimaggio et al., 2015; 2020).

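### Sessions received is a post-randomisation tolerability result, so analysing outcome by it gives a non-randomised and very imprecise association, not evidence of moderation

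*Combined protocol and SAP*

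**What the plan says.** Section 3 (Statistical analysis) ends its paragraph on exploratory regressions with: "Finally, number of sessions received will be examined as a putative moderator". It gives no model, interaction term or cut-off, and does not say whether the treatment effect or simply the amount of change is thought to vary with sessions. The section opens with "As a feasibility study, analyses will be mainly focused on a descriptive method".

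Section 2.7 (Procedure) fixes the order of events. Consent and baseline measures come first, followed by "Participants will then be randomized into two experimental conditions", and only after that: "All participants in each experimental condition will first receive two initial standard sessions". The offer is the same in each arm (section 2.2): "Patients in both conditions will receive 20 weekly sessions of either CBT-E or MIT/CBT-F".

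The aims in section 2.1 are to learn whether the combined treatment is "a) feasible, b) well-tolerated and c) potentially effective on eating disorders symptoms and other outcomes". The Discussion (section 4) says how tolerability is to be judged. The combined arm is expected to be "highly tolerable in terms of session attendance and dropouts".

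Section 2.4 promises dropout rates for each arm. No section names a by-arm summary of sessions attended.

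**The concern.** A moderator should be a characteristic that treatment cannot alter. Both arms are offered the same number of sessions, so the number a patient receives is settled after randomisation by attendance and withdrawal. The sponsor's own hypothesis is that the combined treatment favourably affects both. The same variable is thus a result of treatment in the aims and a moderator of treatment in the analysis.

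The wording allows two readings, and both fail to show moderation. If the arms are compared at different levels of attendance, the groups being compared were formed after randomisation and the comparison loses its protection. If sessions are related to outcome, that too is an observational association: patients who are doing well, or can keep paying for care (section 2.4 says they pay), may attend more.

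At stake is how a pilot signal is used. A finding that the therapy works better with more sessions could be carried into a larger trial when it reflects who stayed, or chance.

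**Working it through.** **No figure to reproduce.** The plan gives 10 + 10 = 20 patients, without a significance level, SD or effect size. What follows assumes two-sided 95% intervals, outcome SD of 1, one time point and every outcome observed, including in dropouts.

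**Dropout inputs.** The Discussion says "We expect possible <10-15% dropouts which would be above the average 17.51% found across evidence-based treatments". The Introduction puts CBT-E dropout at a quarter or more.

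- MIT/CBT-F: 10 × 0.10 = 1.0 to 10 × 0.15 = 1.5, so take 1 to 2.
- CBT-E: 10 × 0.1751 = 1.75 to 10 × 0.25 = 2.5, so take 2 to 3.

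These counts are assumptions. The first range is written with a less-than sign, so fewer is possible; the quarter is a minimum, so more is possible.

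**Precision.** With *a* CBT-E and *b* MIT/CBT-F dropouts:

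- SE of the arm difference in completers = √(1/(10−a) + 1/(10−b))
- SE of the arm difference in dropouts = √(1/a + 1/b)
- SE of the contrast between the two = √(sum of the two squared SEs)
- Unadjusted half-width = t(16 df) × SE = 2.12 × SE
- Baseline-adjusted half-width = t(15 df) × SE × √(1−r²) = 2.13 × SE × √(1−r²), with assumed baseline–outcome correlation r

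| a, b | SE completers | SE dropouts | SE contrast | Half-width, unadjusted | r = 0.5 | r = 0.7 |
|---|---|---|---|---|---|---|
| 2, 1 | 0.49 | 1.22 | 1.32 | 2.79 | 2.43 | 2.01 |
| 3, 1 | 0.50 | 1.15 | 1.26 | 2.67 | 2.33 | 1.92 |
| 2, 2 | 0.50 | 1.00 | 1.12 | 2.37 | 2.06 | 1.70 |
| 3, 2 | 0.52 | 0.91 | 1.05 | 2.22 | 1.94 | 1.60 |

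The unadjusted intention-to-treat difference has SE √(2/10) = 0.447 and half-width 2.10 × 0.447 = 0.94 SD.

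**Bias with no true effect.** In an illustrative large-sample model, a latent prognosis has correlation k with outcome and k with a standard normal dropout tendency. Patients above quantile q drop out, giving dropout proportion d. With higher scores worse, the mean is −k²φ(q)/(1−d) in completers and k²φ(q)/d in dropouts. False arm differences are MIT/CBT-F minus CBT-E. The false moderation is the dropout difference minus the completer difference.

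| Dropout, CBT-E vs MIT/CBT-F | k | Completers | Dropouts | False moderation |
|---|---|---|---|---|
| 17.51% vs 15% | 0.5 | 0.010 | 0.020 | 0.01 |
| 17.51% vs 15% | 0.7 | 0.019 | 0.040 | 0.02 |
| 25% vs 10% | 0.5 | 0.057 | 0.121 | 0.06 |
| 25% vs 10% | 0.7 | 0.112 | 0.237 | 0.13 |

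If the link exists in CBT-E only (k = 0.7, 25% dropout), the two differences are +0.21 and −0.62 SD, a gap of 0.83 SD. The documents give no ground for that case.

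**The case against.** The strongest reply is that this is one putative, exploratory analysis in a mainly descriptive pilot. The Discussion concedes that the small sample may limit what can be seen, and the sentence may mean only that change varies with the amount of therapy. The first two parts stand and keep the point minor. The third does not rescue the label: a sessions–outcome association is also non-randomised. The Discussion's suggestion that mixed models and confidence intervals may ease the small-sample problem does not touch selection after randomisation.

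Three stronger readings are tempting, and the documents support none of them.

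- *The analysis will produce a false moderation signal.* With an equal prognosis–dropout link in both arms, the bias is at most about 0.13 SD in the cases above, far inside the interval. In simulated trials of 10 per arm, a 5% test of the arm-by-sessions term rejected 4.8 to 5.3% of the time under that condition. It rejected 7.7 to 9.8% only with the one-sided link.
- *The half-width must exceed 2 SD.* Section 3 plans baseline adjustment, and with a correlation of 0.5 to 0.7 several cases fall below 2 SD.
- *An arm-by-sessions model often could not be fitted.* With the dropout rates above, the chance that at least one arm has no variation in sessions is 24 to 44% if no completer ever misses one, but 3 to 5% if each completer has a 20% chance of missing at least one. The documents do not say which applies.

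It is also fair to say that the remedy does not cure imprecision. A baseline moderator split 5/5 in each arm would still have SE √(4/5) = 0.89 and half-width 2.12 × 0.89 = 1.9 SD. There is no need for a general rule covering every moderator.

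**Conclusion.** The point holds as a matter of interpretation and precision. Sessions received arises after randomisation and is the protocol's own tolerability measure, so neither reading of the sentence can show moderation. That conclusion needs no numerical assumption.

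The sizes do. The contrast's half-width is about 1.7 to 3 times the unadjusted intention-to-treat figure (1.6/0.94 = 1.7 and 2.8/0.94 = 3.0). This rests on the assumed dropout counts, complete outcome data, a completer/dropout split standing in for the session count, and the assumed baseline correlation where adjustment is used. Bias remains possible but unproven: small under an equal link, material only under a link that differs by arm.

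This is worth considering rather than essential. The planned intention-to-treat comparison is unaffected; the harm is confined to a pilot signal that could be misread.

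**What to change.** Replace the sentence in section 3 with:

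> *Number of sessions attended will be summarised by arm (median, range, number attending all planned sessions) as a tolerability outcome. Any display of outcome by sessions attended will be descriptive, shown by arm and labelled a non-randomised association; it will not be interpreted as moderation of the treatment effect.*

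Also state which sessions count towards the total. Section 2.7 gives every participant two initial standard sessions without saying whether they fall within the 20 for the CBT-E arm, and the end of section 2.7.2 adds a review session two weeks after therapy ends.

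The cost is wording only, since session counts are already needed for the analysis as planned. The plan loses one exploratory model and gains a by-arm attendance summary that its tolerability aim calls for.
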